### **11.5.4 Pharmacokinetics**

The plasma concentrations of betamethasone, betamethasone-17-propionate, and betamethasone-17,21-dipropionate will be summarized (and will include 95% confidence intervals for the mean) for the PK Screening sample and for 0 (pre-treatment), 1, 3, and 6 hours ( $\pm 5$  minutes) after the last application of study product at the end of treatment. The average of the post-treatment concentrations will also be summarized. Plasma concentrations that are taken more than 1 hour off-schedule will be included in data listings only and will not be included in the summarization of the concentration data.

### **11.5.5 Adverse Events**

All AEs occurring during the study will be recorded and classified on the basis of MedDRA terminology. Treatment-emergent adverse events are those AEs with an onset on or after the date of the first study product administration. For the safety population, all reported treatment-emergent AEs will be summarized by treatment group, the number of subjects reporting events, system organ class, preferred term, severity, relationship to study product, and seriousness. When summarizing AEs by causality and severity, each subject will be counted only once within a system organ class or a preferred term by using the event with the greatest relationship and highest severity within each classification.

Serious adverse events (SAEs) will be summarized by treatment group, severity, and relationship to study product, and SAEs will be listed by subject. In addition, a list of subjects who prematurely discontinued from the study due to an AE will be provided.

All information pertaining to AEs noted during the study will be listed by subject, detailing verbatim term given by the investigator, preferred term, system organ class, onset date,

---

resolution date, maximum severity, seriousness, action taken regarding study product, corrective treatment, outcome, and drug relatedness. The event onset will also be shown relative (in number of days) to date of first administration.

AEs related to study procedures done before study product administration will be provided in a data listing.

#### **11.5.6 Vital signs**

Changes from Baseline in vital signs (blood pressure, pulse) will be summarized by treatment group at each evaluation.

#### **11.5.7 Safety Laboratory Values**

Urine pregnancy tests will be performed at all visits for female subjects and will be presented in subject data listings.

#### **11.5.8 Subset Analyses**

No subset analyses are planned.

---

### Declaration of Helsinki (2013)

*Adopted by the 18th WMA General Assembly, Helsinki, Finland, June 1964, and amended by the:*

*29th WMA General Assembly, Tokyo, Japan, October 1975*

*35th WMA General Assembly, Venice, Italy, October 1983*

*41st WMA General Assembly, Hong Kong, September 1989*

*48th WMA General Assembly, Somerset West, Republic of South Africa, October 1996*

*52nd WMA General Assembly, Edinburgh, Scotland, October 2000*

*53rd WMA General Assembly, Washington 2002 (Note of Clarification on paragraph 29 added)*

*55th WMA General Assembly, Tokyo 2004 (Note of Clarification on Paragraph 30 added)*

*59th WMA General Assembly, Seoul, October 2008*

*64th WMA General Assembly, Fortaleza, Brazil, October 2013*

#### A. PREAMBLE

1. The World Medical Association (WMA) has developed the Declaration of Helsinki as a statement of ethical principles for medical research involving human subjects, including research on identifiable human material and data.  
The Declaration is intended to be read as a whole and each of its constituent paragraphs should be applied with consideration of all other relevant paragraphs.
2. Consistent with the mandate of the WMA, the Declaration is addressed primarily to physicians. The WMA encourages others who are involved in medical research involving human subjects to adopt these principles.

#### B. GENERAL PRINCIPLES

3. The Declaration of Geneva of the WMA binds the physician with the words, "The health of my patient will be my first consideration," and the international Code of Medical Ethics declares that, "A physician shall act in the patient's best interest when providing medical care."
4. It is the duty of the physician to promote and safeguard the health, well-being and rights of patients, including those who are involved in medical research. The physician's knowledge and conscience are dedicated to the fulfillment of this duty.
5. Medical progress is based on research that ultimately must include studies involving human subjects.
6. The primary purpose of medical research involving human subjects is to understand the causes, development and effects of diseases and improve preventive, diagnostic and therapeutic interventions (methods, procedures and treatments). Even the best current interventions must be evaluated continually through research for their safety, effectiveness, efficiency, accessibility and quality.
7. Medical research is subject to ethical standards that promote and ensure respect for all human subjects and protect their health and rights.
8. While the primary purpose of medical research is to generate new knowledge, this goal can never take precedence over the rights and interests of individual research subjects.
9. It is the duty of physicians who are involved in medical research to protect the life, health, dignity, integrity, right to self-determination, privacy, and confidentiality of personal information of research subjects. The responsibility for the protection of research subjects must always rest with the physician or other health care professionals and never with the research subjects, even though they have given consent.
10. Physicians must consider the ethical, legal and regulatory norms and standards for research involving human subjects in their own countries as well as applicable international norms and standards. No national or international ethical, legal or regulatory requirement should reduce or eliminate any of the protections for research subjects set forth in this Declaration.
11. Medical research should be conducted in a manner that minimizes possible harm to the environment.

12. Medical research involving human subjects must be conducted only by individuals with the appropriate ethics and scientific education, training and qualifications. Research on patients or healthy volunteers requires the supervision of a competent and appropriately qualified physician or other health care professional.
13. Groups that are underrepresented in medical research should be provided appropriate access to participation in research.
14. Physicians who combine medical research with medical care should involve their patients in research only to the extent that this is justified by its potential preventive, diagnostic or therapeutic value and if the physician has good reason to believe that participation in the research study will not adversely affect the health of the patients who serve as research subjects.
15. Appropriate compensation and treatment for subjects who are harmed as a result of participating in research must be ensured.

**C. RISK, BURDENS AND BENEFITS**

16. In medical practice and in medical research, most interventions involve risks and burdens. Medical research involving human subjects may only be conducted if the importance of the objective outweighs the risks and burdens to the research subjects.
17. All medical research involving human subjects must be preceded by careful assessment of predictable risks and burdens to the individuals and groups involved in the research in comparison with foreseeable benefits to them and to other individuals or groups affected by the condition under investigation. Measures to minimize the risks must be implemented. The risks must be continuously monitored, assessed and documented by the researcher.
18. Physicians may not be involved in a research study involving human subjects unless they are confident that the risks have been adequately assessed and can be satisfactorily managed. When the risks are found to outweigh the potential benefits or when there is conclusive proof of definitive outcomes, physicians must assess whether to continue, modify or immediately stop the study.

**D. VULNERABLE GROUPS AND INDIVIDUALS**

19. Some groups and individuals are particularly vulnerable and may have an increased likelihood of being wronged or of incurring additional harm.

All vulnerable groups and individuals should receive specifically considered protection.

20. Medical Research with a vulnerable group is only justified if the research is responsive to the health needs or priorities of this group and the research cannot be carried out in a non-vulnerable group. In addition, this group should stand to benefit from the knowledge, practices or interventions that result from the research.

**E. SCIENTIFIC REQUIREMENTS AND RESEARCH PROTOCOLS**

21. Medical research involving human subjects must conform to generally accepted scientific principles, be based on a thorough knowledge of the scientific literature, other relevant sources of information, and adequate laboratory and, as appropriate, animal experimentation. The welfare of animals used for research must be respected.
22. The design and performance of each research study involving human subjects must be clearly described and justified in a research protocol. The protocol should contain a statement of the ethical considerations involved and should indicate how the principles in this Declaration have been addressed. The protocol should include information regarding funding, sponsors, institutional affiliations, potential conflicts of interest, incentives for subjects and information regarding provisions

---

for treating and/or compensating subjects who are harmed as a consequence of participation in the research study. In clinical trials, the protocol must also describe appropriate arrangements for post-trial provisions.

#### F. RESEARCH ETHICS COMMITTEES

23. The research protocol must be submitted for consideration, comment, guidance and approval to the concerned research ethics committee before the study begins. This committee must be transparent in its functioning, must be independent of the researcher, the sponsor and any other undue influence and must be duly qualified. It must take into consideration the laws and regulations of the country or countries in which the research is to be performed as well as applicable international norms and standards but these must not be allowed to reduce or eliminate any of the protections for research subjects set forth in this Declaration. The committee must have the right to monitor ongoing studies. The researcher must provide monitoring information to the committee, especially information about any serious adverse events. No amendment to the protocol may be made without consideration and approval by the committee. After the end of the study, the researchers must submit a final report to the committee containing a summary of the study's findings and conclusions.

#### G. PRIVACY AND CONFIDENTIALITY

24. Every precaution must be taken to protect the privacy of research subjects and the confidentiality of their personal information.

#### H. INFORMED CONSENT

25. Participation by individuals capable of giving informed consent as subjects in medical research must be voluntary. Although it may be appropriate to consult family members or community leaders, no individual capable of giving informed consent may be enrolled in a research study unless he or she freely agrees.
26. In medical research involving human subjects capable of giving informed consent, each potential subject must be adequately informed of the aims, methods, sources of funding, any possible conflicts of interest, institutional affiliations of the researcher, the anticipated benefits and potential risks of the study and the discomfort it may entail, post-study provisions and any other relevant aspects of the study. The potential subject must be informed of the right to refuse to participate in the study or to withdraw consent to participate at any time without reprisal. Special attention should be given to the specific information needs of individual potential subjects as well as to the methods used to deliver the information. After ensuring that the potential subject has understood the information, the physician or another appropriately qualified individual must then seek the potential subject's freely-given informed consent, preferably in writing. If the consent cannot be expressed in writing, the non-written consent must be formally documented and witnessed. All medical research subjects should be given the option of being informed about the general outcome and results of the study.
27. When seeking informed consent for participation in a research study the physician should be particularly cautious if the potential subject is in a dependent relationship with the physician or may consent under duress. In such situations the informed consent should be sought by an appropriately qualified individual who is completely independent of this relationship.
28. For a potential research subject who is incapable of giving informed consent, the physician must seek informed consent from the legally authorized representative. These individuals must not be included in a research study that has no likelihood of benefit for them unless it is intended to promote the health of the group represented by the potential subject, the research cannot instead be performed with persons capable of providing informed consent, and the research entails only minimal risk and minimal burden.
29. When a potential research subject who is deemed incapable of giving informed consent is able to give assent to decisions about participation in research, the physician must seek that assent in addition to

the consent of the legally authorized representative. The potential subject's dissent should be respected.

30. Research involving subjects who are physically or mentally incapable of giving consent, for example, unconscious patients, may be done only if the physical or mental condition that prevents giving informed consent is a necessary characteristic of the research group. In such circumstances the physician must seek informed consent from the legally authorized representative. If no such representative is available and if the research cannot be delayed, the study may proceed without informed consent provided that the specific reasons for involving subjects with a condition that renders them unable to give informed consent have been stated in the research protocol and the study has been approved by a research ethics committee. Consent to remain in the research should be obtained as soon as possible from the subject or a legally authorized representative.
31. The physician must fully inform the patient which aspects of their care are related to the research. The refusal of a patient to participate in a study or the patient's decision to withdraw from the study must never adversely affect the patient-physician relationship.
32. For medical research using identifiable human material or data, such as research on material or data contained in biobanks or similar repositories, physicians must seek informed consent for its collection, storage and/or reuse. There may be exceptional situations where consent would be impossible or impracticable to obtain for such research. In such situations the research may be done only after consideration and approval of a research ethics committee.

#### I. USE OF PLACEBO

33. The benefits, risks, burdens and effectiveness of a new intervention must be tested against those of the best proven intervention(s), except in the following circumstances:
  - a. Where no proven intervention exists, the use of placebo, or no intervention, is acceptable; or
  - b. Where for compelling and scientifically sound methodological reasons the use of any intervention less effective than the best proven one, the use of placebo, or no intervention is necessary to determine the efficacy or safety of an intervention and the patients who receive any intervention less effective than the best proven one, placebo, or no intervention will not be subject to additional risks of serious or irreversible harm as a result of not receiving the best proven intervention. Extreme care must be taken to avoid abuse of this option.

#### J. POST-TRIAL PROVISIONS

34. In advance of a clinical trial, sponsors, researchers and host country governments should make provisions for post-trial access for all participants who still need an intervention identified as beneficial in the trial. This information must also be disclosed to participants during the informed consent process.

#### K. RESEARCH REGISTRATION AND PUBLICATION AND DISSEMINATION OF RESULTS

35. Every research study involving human subjects must be registered in a publicly accessible database before recruitment of the first subject.
36. Researchers, authors, sponsors, editors and publishers all have ethical obligations with regard to the publication and dissemination of the results of research. Researchers have a duty to make publicly available the results of their research on human subjects and are accountable for the completeness and accuracy of their reports. All parties should adhere to accepted guidelines for ethical reporting. Negative and inconclusive as well as positive results must be published or otherwise made publicly available. Sources of funding, institutional affiliations and conflicts of interest should be declared in the publication. Reports of research not in accordance with the principles of this Declaration should not be accepted for publication.
37. In the treatment of an individual patient, where proven interventions do not exist or other known interventions have been ineffective, the physician, after seeking expert advice, with informed consent from the patient or a legally authorized representative, may use an unproven intervention if in the physician's judgment it offers hope of saving life, re-establishing health or alleviating suffering. This

---

intervention should subsequently be made the object of research, designed to evaluate its safety and efficacy. In all cases, new information must be recorded and, where appropriate, made publicly available.

October 2013

---

**APPENDIX 2**  
**Subject Instructions - Spray**

1. You have been given a bottle of study medication. **Shake well before using.** Spray study medication directly onto each of your psoriasis lesions as instructed by the study nurse. Refer to the diagram provided. Apply study medication to all areas shown on the body diagram even if clear. Also apply study medication to new areas that may appear between visits. Apply study medication in the morning and at bedtime, approximately 12 hours apart. You will need to use at least 15-20 sprays of study medication each time. You can use more if needed. Massage lightly after application until medication disappears. If bathing at the treatment time, apply medication after bathing.
2. The study medication is for external use only. The study medication should not be used on the scalp, face, underarms, or groin area. Also avoid contact with eyes and lips. The application areas must not be bandaged, covered, or wrapped.
3. Always wash hands before applying the study medication and thoroughly after applying.
4. Store medication at room temperature.
5. If you have any questions, please ask the study coordinator or nurse.
6. The study medication may cause some irritation or discomfort. Tell your doctor about any reactions. If the reaction becomes severe, stop using the study medication and call the doctor.
7. Write down the date and time (am or pm) when you apply the study medication in your study diary.
8. Do not let anyone else use the study medication. Keep the medication out of the reach of children and pets. Use of the study product should be done under the supervision of the legal guardian.
9. Return all containers in the box at every study visit.
10. Bring your study diary to every visit.
11. If you cannot make a scheduled visit, please contact the study office as soon as possible to re-schedule another date.
- 12. Do not use study medication on the morning of your last study visit.**
13. If you have to discontinue participation in the study for any reason, notify the study office immediately. A visit will be scheduled for a final examination of psoriasis and to collect the containers and your diary. This visit is important for your safety.

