**Investigational Product, Dose and Mode of Administration:**

---

DFD-01 (betamethasone dipropionate) Spray, 0.05%

The investigational product will be applied topically to all affected areas (i.e., those areas that were affected at Baseline, even if resolved, and new lesions that develop at any time during the treatment period) twice daily, approximately 12 hours apart. The target dose is at least 3 to 5 g per day (10 to 15 pumps, twice daily). Product is not to be applied to face, scalp, groin, axillae, or other intertriginous areas.

---

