## **6.2 Treatment Regimen**

Subjects will use study product under the supervision and with help, if needed, of their legal guardian, twice daily with approximately 12 hours between applications for either 15 or 29 days starting on Day 1 during the study visit. Subjects will apply study product to all affected areas except the face, scalp, groin, axillae and other intertriginous areas. The target dose is at least 3 to 5 g per day (10 to 15 pumps of spray), twice daily, applied at approximately 2 mg/cm^2 on 10% BSA – 1500 cm^2). Subjects with greater than 10% BSA will apply more, as appropriate. All baseline affected areas and newly affected areas should be treated until the end of the study even if cleared. The investigator shall diagram the affected areas (in the source document), update the diagram at each visit, and remind the subjects and legal guardians where study product is to be applied at each visit using the diagram. Study product should be sprayed directly onto affected areas and rubbed in gently and completely. Study product should be applied after bathing, if applicable.

The first and last dates of treatment should be recorded in the CRF with the number of applications made on those days.

The first and last application of study product will be applied by the subjects or their legal guardian at the site under supervision. At the last visit, the bottle should be weighed before and after the application to determine the amount of study product applied for the last dose.

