## **6.3 Treatment and Protocol Compliance**

Subjects and legal guardians will be provided an instruction sheet specific for the study product, along with a diagram of affected areas to be treated. Study staff should review the instruction sheet and diagram with the subjects and their legal guardian to ensure protocol compliance. If new affected areas appear between visits, the subject may start treating the new area between visits. Treatment areas are to be updated on the diagram at each visit.

At each visit, the investigator or designee will interview subjects and their legal guardian concerning treatment compliance and ask if any doses have been missed. The investigator will also ask about compliance with protocol requirements. Protocol deviations will be recorded in the subject's chart and Protocol Deviation Form. A Protocol Deviation Form is not needed for

---

missed visits, missed applications, out-of-window visits and missing data. These items will be apparent from the missing data on the CRF and will be identified programmatically during data analysis for purposes of reporting. The sponsor should be consulted before discontinuing subjects due to protocol deviations unless safety is a concern.

Subjects/legal guardian will be provided a diary card for documenting the dates of applications. The subjects and legal guardian will review the diary card with the investigator or designee at each visit. The number of applications and the number of missed applications will be recorded on the CRF. By definition, there are no missed applications after the last date of treatment even if recorded on the diary.

In addition, bottles of study product will be weighed before dispensing and before and after the last application. These weights should be entered into the CRF.

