### **7.9.2 Visit 2 - Day 1 - Baseline Visit**

1. Update the medical history and concomitant medications. Any medical event (not related to a protocol intervention) that occurred since informed consent was signed should be recorded as medical history if still ongoing.
2. Collect adverse events. Any new medical event, need for new medication, or change in medication dosing caused by a protocol procedure performed at the Screening Visit should

be considered an adverse event except for worsening of psoriasis.

3. Confirm eligibility according to inclusion/exclusion criteria.
4. Conduct urine pregnancy test on female subjects. Record method of contraception, as applicable, on source only.
5. Collect vital signs (blood pressure, pulse).
6. Conduct clinical assessments:
  - a. IGA ([Table 2](#))
  - b. Local cutaneous safety evaluation for clinically significant atrophy and telangiectasia in areas to be treated. The investigator should also ask the subject if any burning/stinging, pain, or itching has occurred in the areas to be treated in the last 14 days.
  - c. Diagram affected areas to be treated (excluding face, scalp, axillae, groin and other intertriginous areas).
  - d. Determine BSA excluding face, scalp, axillae, groin and other intertriginous areas.
7. Randomize the subject by referring to the randomization schedule and dispense study product to the subject/legal guardian. The tear-off panel from the box is to be affixed to the source document. Make a note on source document regarding treatment duration.
8. Instruct subject and legal guardian on study product use. Review the appropriate Subject Instructions with subject (See [Appendix 2](#)). Using the diagram of affected areas, have the subject treat the affected areas under supervision after weighing the study product.
9. Dispense and review use of diary. Remind subject and legal guardian to record actual application dates and/or potential adverse events as well as any medication used in the diary and to bring diary to each visit.
10. Schedule next visit.
11. Complete CRF for all subjects including screen failures. Only enter concurrent medical conditions and concomitant medications on the CRF.

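### The subject instruction sheet leaves other intertriginous areas off its list of excluded sites, so a new skin-fold lesion could be treated where Section 6.2 bars it

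*Combined protocol and SAP*

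**What the plan says.** The protocol body is consistent about where the spray may go. Section 6.2 states: "Subjects will apply study product to all affected areas except the face, scalp, groin, axillae and other intertriginous areas". The synopsis, under investigational product, says the same: "Product is not to be applied to face, scalp, groin, axillae, or other intertriginous areas". The synopsis methods and Section 4 repeat the list. At the Baseline Visit (Section 7.9.2) the treatment map is drawn under the same rule: "Diagram affected areas to be treated (excluding face, scalp, axillae, groin and other intertriginous areas".

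Appendix 2, which the subject and guardian use at home, has a shorter list in item 2: "The study medication should not be used on the scalp, face, underarms, or groin area". Item 1 of the sheet adds: "Also apply study medication to new areas that may appear between visits".

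Treating new lesions between visits is also the protocol's own rule. Section 6.3 says: "If new affected areas appear between visits, the subject may start treating the new area between visits". It then says of the map: "Treatment areas are to be updated on the diagram at each visit".

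**The concern.** The sheet is a working instruction. Section 6.3 has staff go through it with subjects and guardians to secure compliance, and the bottle and box labels refer only to use as instructed. Of the take-home texts reproduced in the protocol, it is the only one that names excluded sites. If its list is shorter than the protocol's, a family can follow it faithfully and still depart from Section 6.2.

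The consequence would be application of a corticosteroid at sites the protocol excludes, with possible local effects; atrophy and telangiectasia are tracked under Section 7.5.2. The area treated would also differ from the recorded BSA, because Sections 7.3, 7.9.2 and 7.9.5 measure BSA without intertriginous areas.

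**Working it through.** The protocol gives no figure to reproduce. The check is a comparison of texts, followed by a count of applications.

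**1. The two lists.**

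| Site | Synopsis, Sections 4 and 6.2 | Appendix 2, item 2 |
|---|---|---|
| Face | excluded | excluded |
| Scalp | excluded | excluded |
| Groin | excluded | excluded |
| Axillae / underarms | excluded | excluded |
| Other intertriginous areas | excluded | not mentioned |

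That is five categories against four. Neither the technical term nor a lay equivalent such as skin folds appears anywhere on the sheet.

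**2. Does the diagram close the gap?** For lesions present at Baseline, yes: Section 7.9.2 draws the map with all five exclusions, and item 1 of the sheet refers to it. For a lesion that appears later, no: the map cannot show it until the next visit.

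The two study schedules place diagram steps as follows:
- 15-day arm: Visits 2 and 3, so the last update is Day 8.
- 29-day arm: Visits 2, 3 and 4, so the last update is Day 15.
- End of Treatment Visit: none in either arm, and none in Section 7.9.5.

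A fold lesion that arises after the last update never reaches the map. The update steps in Sections 7.9.3 and 7.9.4 do not repeat the exclusion list.

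**3. Result for one case.** Take a new lesion in a fold other than underarm or groin, appearing between visits. Under the sheet it is a new area to be treated and is not on the excluded list. Under Section 6.2 it is excluded. The two texts give different answers.

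**4. Applications in one interval.** Formula: days between visits × 2 applications per day.
- Day 1 to Day 8, and Day 8 to Day 15 (both arms): 7 × 2 = 14.
- Day 15 to Day 29 (29-day arm only): 14 × 2 = 28.

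The ±3-day windows can lengthen these intervals:
- Day 1 to Day 11: 10 × 2 = 20.
- Day 5 to Day 18: 13 × 2 = 26.
- Day 12 to Day 32 (29-day arm only): 20 × 2 = 40.

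These are ceilings for the interval concerned. They assume that the lesion appears just after one visit and receives every dose until the next. In the last interval the count includes the final application, which is supervised at the clinic.

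**5. What cannot be computed.** The documents do not say how many subjects have, or would develop, lesions in other folds. They also give no figure for absorption from such sites. No change in the proportion suppressed or in plasma concentrations can be derived.

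**The case against.** The case for leaving this alone is reasonable. The sheet does not stand by itself: item 1 points to the nurse's instruction and to the diagram. The investigator reminds subject and guardian at each visit where to apply (Section 6.2), staff review sheet and diagram with them (Section 6.3), and the first application is supervised on site. The sheet also requires a guardian: "Use of the study product should be done under the supervision of the legal guardian". Enrolment needs plaque psoriasis stable for at least 3 months, and treatment lasts only 15 or 29 days, so new fold lesions may be few. All of this stands, and it makes the gap narrow. It does not remove it, because the guardian works from the same short list and the map cannot show a lesion that was absent when it was drawn.

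A reader might infer more than the documents support:

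- **That the sheet permits use in skin folds.** It does not say so. The conflict arises by omission.
- **That telling subjects to treat new areas breaks the protocol.** The synopsis and Section 6.3 allow it. Only the exclusion list differs.
- **That these applications are unsupervised.** Section 6.2 and the sheet call for guardian supervision. They are made without site staff present, which is a different matter.
- **That exposure per treated area would be misreported.** Section 11.5.1 plans no such analysis. It summarises number of applications, total product by bottle weight and the weight of the last dose, and bottle weight captures product wherever it is applied. A new lesion at a permitted site also lies outside Baseline BSA, by design.
- **That local effects in a treated fold would go unseen.** Section 7.5.2 has the investigator examine treated areas, which would include such a fold.

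**Conclusion.** The point holds as a minor internal inconsistency, wrong as written. Appendix 2 item 2 omits one of the five excluded categories in the synopsis and Section 6.2, and the diagram does not make up the difference for lesions that appear between visits.

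It is confined to new lesions in folds other than underarm and groin. The ceiling is 14 applications over a scheduled 7-day interval, or 28 over the last interval of the 29-day arm, before any lengthening by visit windows. These counts assume twice-daily use without missed doses and onset immediately after a visit.

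The supported consequence is possible application at sites that the protocol excludes, with possible local effects and a treated area that recorded BSA does not reflect. No planned analysis is shown to be affected, and nothing in the documents supports a claim about the suppression rate or the plasma concentrations.

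**What to change.** Reconcile the synopsis, Section 6.2 and Appendix 2 item 2 so that the protocol and the subject sheet carry the same list of excluded areas. Which list is intended is for the sponsor to confirm. The sheet should state it in words that an adolescent and guardian can follow. Repeating the list beside the new-area sentence in item 1 would help, but is optional.

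The cost is a line or so of text, approval of the revised subject material by the IRB under Section 2.1, and replacement of the copies held at sites. No change to sample size, visits, data collection or the planned summaries is needed.
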